3.4. Baseline Variables

3.4.1. Covariates and Stratification Variables

- Baseline for the primary endpoint: Baseline NSAA total score is defined as the last non-missing NSAA total score collected prior to Year 1 IP administration.
- Baseline for secondary and exploratory endpoints: Baseline is defined as the last non-missing assessment collected prior to Year 1 IP administration.
- Screening age (years) covariate: The screening age covariate is defined as the participant's age (as calculated based on month and year of birth) on the day of the Screening visit. Screening age will be calculated to one decimal (eg, 7 years and 4 months will be 7.3 years).
- The participant's Screening age rather than Screening age stratum will be used in all efficacy analyses, unless specified otherwise.

3.4.2. Other Baseline Variables to be Summarized

1. Demographic characteristics including age, gender, race, and ethnicity, where age is calculated as age in years at the Screening visit.
2. Age (years) at dosing with IP on Year 1 Day 1, where age is calculated and rounded to one decimal.
3. Screening age strata (<6 or ≥ 6 years old): Screening age strata will be based on the randomization group entered in CRF by a site that identifies the age strata for a participant based on age at screening.
4. Physical measurements at Baseline include height (cm) and weight (kg) where Baseline is defined as the last non-missing assessment collected prior to Day 1 (Year 1 Day 1).
5. Other participant characteristics including:
 - Details of DMD genetic results.
 - Background glucocorticoid regimen (including specific medication and daily dose in mg/kg, and duration of current glucocorticoid regimen use) at the Screening visit, and age at initiation of any glucocorticoid use (years/months).
 - Duration of glucocorticoid use (months) for the glucocorticoid regimen the participant was receiving at Screening.
 - Age at initiation of any glucocorticoid use.
 - Enrollment geographical region (eg, North America, Western Europe, Eastern Europe, and Asia) and country within each region.

6. General medical history, including diseases or syndromes that are stopped before Screening (“before”) or ongoing (“ongoing”). The Medical Dictionary for Regulatory Activities (MedDRA) will be used to code the disease/syndrome.
7. Medications taken prior to the first dose.

3.5. Safety Endpoints

For safety endpoints, unless otherwise specified, Baseline is defined as the last non-missing assessment collected prior to Day 1 (Year 1 Day 1) IP administration. For vital signs, baseline is defined as the assessment collected prior to dosing (0 minutes) on Day 1.

3.5.1. Adverse Events

All nonserious AEs and SAEs occurring in a participant during the active collection period, which begins after obtaining informed consent as described in Section 8.3.1.2 of the protocol, will be recorded on the AE section of the CRF. MedDRA will be used to classify all AEs with respect to system organ class (SOC) and preferred term (PT).

An AE is considered a treatment-emergent adverse event (TEAE) if the event started during the reporting period for the Primary Analysis through Week 52 ([Section 2.3.2](#)).

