2.3.2. Treatment Groups and Reporting Periods for Analysis

In the study schematic in Figure 1, the study period and treatment groups to be included in the primary analysis are encircled in red.

- Treatment groups:
 1. fordadistrogene movaparvovec – participants randomized to Cohort 1 to receive a single dose of fordadistrogene movaparvovec on Day 1 (Year 1 Day 1).
 2. Placebo – participants randomized to Cohort 2 to receive a single dose of placebo on Day 1 (Year 1 Day 1).

- Reporting Period:

All analyses will be relative to Day 1 (Year 1 Day 1) investigational product (IP) administration.

The reporting period will include all data from the day of the Year 1 Day 1 IP administration through Week 52. Specifically, all participant data from Day 1 to the earliest of (1) Day 390 (the upper limit of the Week 52 analysis visit window or (2) one day before the Year 2 Day 1 IP administration.

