6.7.1. Adverse Events

Incidence of TEAEs (all-causality and treatment-related) in the reporting period will be summarized by SOC, PT, and severity for fordadistrogene movaparvovec and placebo. Adverse events may be clustered to reflect medical concepts.

A summary of the TEAEs (all-causality and treatment-related) occurring during the reporting period will be tabulated by PT sorted by decreasing incidence for fordadistrogene movaparvovec and placebo. The most commonly reported TEAEs will be summarized using those PTs with high frequency (cutoff depends on the final frequency of TEAEs) for fordadistrogene movaparvovec-dosed participants in the safety analysis set.

Deaths and SAEs will be listed and incidence of SAEs(all causality and treatment-related) will be summarized by SOC and PT for fordadistrogene movaparvovec and placebo.

A summary of the SAEs (all-causality and treatment-related) occurring during the reporting period will be tabulated by PT sorted by decreasing incidence for fordadistrogene movaparvovec and placebo. The most commonly reported SAEs will be summarized using those PTs with high frequency (cutoff depends on the final frequency of serious TEAEs) for fordadistrogene movaparvovec-dosed participants in the safety analysis set.

For each participant who reported a TEAE (all-causality or onset treatment-related), the time (in days) to (date of onset of the event - date of dosing + 1) for that TEAE will be summarized by PT as continuous data. Participants with multiple TEAEs will be included multiple times in the summary statistics. Events that occur on the day of dosing will have a time of onset as day 1.

For each participant who reported a serious TEAE (all-causality or treatment-related), the time (in days) to onset (date of onset of the event - date of dosing + 1) for that serious TEAE will be summarized by PT as continuous data. Participants with multiple serious TEAEs will be included multiple times in the summary statistics. Events that occur on the day of dosing will have a time of onset as Day 1.

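### The TEAE rule looks only at the start date, so an AE that began before dosing and worsened afterwards is left out unless the protocol records the worsening as a new event

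*SAP*

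**What the plan says.** The TEAE rule in SAP Section 3.5.1 is one sentence: "An AE is considered a treatment-emergent adverse event (TEAE) if the event started during the reporting period for the Primary Analysis through Week 52". The same section says that AEs are recorded over an active collection period "which begins after obtaining informed consent as described in Section 8.3.1.2 of the protocol".

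Section 2.3.2 fixes the period: "The reporting period will include all data from the day of the Year 1 Day 1 IP administration through Week 52". In detail it covers "all participant data from Day 1 to the earliest of (1) Day 390" or the day before the Year 2 Day 1 infusion.

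Section 6.7.1 builds its main tables on this flag: incidence by system organ class, preferred term and severity, tables sorted by frequency, and time to onset. Onset is computed from dates as "date of onset of the event - date of dosing + 1", and "Events that occur on the day of dosing will have a time of onset as day 1".

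No sentence in the SAP deals with an AE that was present before dosing and then worsened.

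**The concern.** The safety objective in Section 2.2 covers the incidence, severity and causal relationship of treatment-emergent events. A rule that reads only the start date cannot register a rise in severity, or a change to serious, in an AE that was already open at dosing.

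The window for such AEs runs from consent to infusion. Section 6.1.1.5 acknowledges that pauses in dosing separated age at screening from age at dosing, so for some boys this window may have been long.

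For some kinds of harm the AE tables are the only summary. Section 6.7.5 plans no summaries of physical or neurological examinations and sends clinically significant findings to the AE tables. If an AE of that kind began before dosing and worsened afterwards, the TEAE comparison between arms would not show it.

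**Working it through.** There is no planned figure to reproduce, so the check applies the written rule to cases. The inputs are the start-date rule (3.5.1), the period (2.3.2) and the onset formula (6.7.1). The days are illustrative.

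- **Case A: an AE starts five days before dosing as mild and becomes severe five days after dosing.** Onset day = −5 + 1 = −4, which is before Day 1. The start lies outside the period, so it is not a TEAE. The worsening falls on day 5 + 1 = 6, inside the period, but the rule does not use that date.
- **Case B: the same event, but the protocol has the worsening entered as a new AE.** The new record starts on Day 6 and is a TEAE. The gap closes.
- **Case C: a condition listed as ongoing medical history (3.4.2) worsens on Day 6 and is reported as an AE.** That AE starts on Day 6 and is a TEAE. Nothing in the SAP backdates it to the start of the underlying condition.
- **Case D: an AE starts on Day 1 before the infusion.** Onset day = 0 + 1 = 1, so it is a TEAE.
- **Case E: an AE starts on Day 1 after the infusion.** Onset day = 0 + 1 = 1, so it is a TEAE that dates alone cannot separate from Case D.

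Case A is the defect. Cases B and C mark its limits. Cases D and E are a lesser issue, and the SAP does use infusion time elsewhere: in Section 3.5, "For vital signs, baseline is defined as the assessment collected prior to dosing (0 minutes) on Day 1". An observation made on Day 1 before dosing is thus baseline for vital signs but treatment-emergent for AEs.

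The rest of the SAP was then read for anything that would bring Case A back:

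- **SAEs (6.7.1).** The listing and the incidence tables are not expressly limited to TEAEs, and one table covers SAEs occurring in the reporting period. A Case A event that becomes serious may appear there. The time-to-onset summary, however, is for serious TEAEs.
- **AEs of interest (6.7.1).** These are summarised as all-causality AEs and SAEs, again without the TEAE condition. The peri-infusion group (onset Day 1 through Day 14) and the late-onset group (after Week 4) are set by onset date, so Case A would enter neither.
- **Direct measurements (6.7.2 to 6.7.4, 6.7.6, 6.7.7).** Laboratory abnormalities are split by baseline status, some parameters have shift tables, and vital signs, ECG, echocardiogram and cardiac MRI have changes from baseline. These show worsening in what they measure.

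None of these outputs gives a between-arm incidence for a non-serious clinical AE, outside the list of AEs of interest, that began before dosing and worsened after it.

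**The case against.** The strongest objection is that how a worsening is recorded belongs to the protocol and the CRF. If site instructions require a new AE record when severity increases, the start-date rule already captures it. This stands as a condition on the point. It does not remove the point, because Section 3.5.1 cites the protocol only for the collection period and the TEAE sentence reads as complete.

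A reader might also infer more than the SAP supports:

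- **That worsening of chronic disease in general is lost.** Ongoing conditions sit in medical history and have no pre-dose AE start date. The gap concerns AEs that began between consent and dosing.
- **That every AE table is affected, or that nothing shows a worsening.** The SAE and AE-of-interest outputs are not expressly tied to the TEAE flag, and the measured safety parameters show some worsening directly.
- **That a number of boys can be stated.** The SAP gives no rate of AEs open at dosing and no rate of worsening. Any count would only return the rates assumed.
- **That pre-infusion Day 1 events distort the comparison.** They span a few hours, arise in both arms of a double-blind trial and mainly add noise. Separating them needs AE start times, which the SAP does not show are collected.

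**Conclusion.** The point holds in a bounded form. As written, the rule excludes an AE that began between consent and Year 1 dosing and then increased in severity or became serious, unless the protocol turns the worsening into a new record. The affected outputs are the main TEAE incidence-by-severity and time-to-onset summaries.

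The error would understate post-dose incidence and severity. If the vector caused such worsening, it would also understate the difference between arms. The size cannot be derived. It depends on the share of boys with an AE open at dosing, the share of those AEs that worsen, and the recording rule, and the SAP gives none of the three. The efficacy analyses do not use the TEAE flag and are unaffected.

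The worsening clause carries the point; the Day 1 timing is secondary. The definition should be corrected because the change is cheap and bears directly on the stated safety endpoint.

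**What to change.** In Section 3.5.1, define a TEAE as an AE that either

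1. starts within the reporting period, or
2. started before Year 1 Day 1 IP and increases in severity or becomes serious during the reporting period, with onset dated from the worsening.

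Add that a Day 1 event with a recorded start time before the infusion is pre-treatment, and that a Day 1 event without a time counts as a TEAE. If the protocol already has worsenings entered as new AEs, say so and cite the section. Clause 2 then serves as a safeguard, and the derivation must not count the same worsening twice.

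The cost is one extra derivation and slightly higher TEAE counts. Clause 2 needs the date on which severity rose or the event became serious, so confirm that the CRF holds it. No new analysis or design change is needed. The change should be made before unblinding.

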3.5.2. Laboratory Data

The following safety laboratory tests will be collected. Analyses for banked biospecimens are not in scope for this SAP.

Table 2. Protocol Required Safety Laboratory Assessments

CENTRAL LABORATORY TESTING		
Clinical Safety		
Hematology	Urinalysis	Other
Hemoglobin Hematocrit Red blood cell (RBC) count and morphology Platelet count White blood cell count (and morphology as applicable) Total neutrophils (Abs) Absolute neutrophils Eosinophils (Abs) Monocytes (Abs) Basophils (Abs) Lymphocytes (Abs) Red blood cell indices (mean corpuscular volume, mean corpuscular hemoglobin, mean corpuscular hemoglobin concentration)	PH Glucose (qual) Protein (qual) Blood (qual) Ketones Nitrites Leukocyte esterase Microscopy and culture ⁰	Prothrombin time (PT) activated partial thromboplastin time C-reactive protein Lipase Amylase Cystatin C Haptoglobin ^b
Chemistry and Hepatic Safety		
BUN and Creatinine Glucose Calcium Sodium Potassium Chloride Total CO2 (Bicarbonate) AST, ALT Total Bilirubin (direct and indirect bilirubin) Alkaline phosphatase Uric Acid Albumin Total protein Serum Phosphorus Gamma glutamyl transferase (GGT) Glutamate dehydrogenase (GLDH)		
For Screening (Visit 1) and Day 360 (Visit 19) Only		
International normalized ratio (INR) Hepatitis A virus (anti-HAV) immunoglobulin M Hepatitis B surface antigen Hepatitis C antibody		
For Post IP Intensified Safety Monitoring (at Year 1 and Year 2)		
Complement biomarkers eg, C3 and C4, additional exploratory ^c Haptoglobin – analyzed by local laboratory on Days 2 and 4 (Visits 4 and 5) in Year 1 and on Days 391 and 393 (Visits 21 and 22) in Year 2 for sites in Japan. Urine biomarkers		

Table 2. Protocol Required Safety Laboratory Assessments

Other Assessments	
Immunogenicity: NAb to AAV9; ELISpot to AAV9; ADA to AAV9; ELISpot to mini-dystrophin; ADA to mini-dystrophin	
Viral vector shedding (whole blood, saliva, and urine)	
Cardiac troponin I	
Creatine kinase	
Conditional Testing	
Genetic screening for aHUS-Central Laboratory , if needed as per Section 6.5.1 in the Protocol	
Local assessment of NT-ProBNP/BNP , if needed as per Section 8.2.7 in the Protocol	
LOCAL AND CENTRAL LABORATORY TESTING	
Local Laboratory	
Hematology: as per clinical safety panel, including blood smear for morphology. Absolute neutrophils are not required	Day 6 to 10 (Visits 6 to 10) in Year 1 Day 395 to 399 (Visits 23 to 27) in Year 2
Chemistry and hepatic safety: at a minimum, creatinine, BUN(or blood urea if BUN cannot be performed), calcium, sodium, potassium, chloride, total CO ₂ (bicarbonate), uric acid and serum phosphorus; but excluding AST and ALT- sensitive clinical data	Day 6 to 10 (Visits 6 to 10) in Year 1 Day 395 to 399 (Visits 23 to 27) in Year 2
Cystatin C (when possible)	Day 6 to 10 (Visits 6 to 10) in Year 1 Day 395 to 399 (Visits 23 to 27) in Year 2
Urinalysis: as per clinical safety panel	Day 6 to 10 (Visits 6 to 10) in Year 1 Day 395 to 399 (Visits 23 to 27) in Year 2
Cardiac troponin I, (or cardiac troponin T if cardiac troponin I is not available)	Baseline Visit (Visit 2), Day 2 (Visit 4), Day 4 (Visit 5), Day 6 (Visit 6), Day 8 (Visit 8), and Day 10 (Visit 10) in Year 1 Day 390 (Visit 20), Day 391 (Visit 21), Day 393 (Visit 22), Day 395 (Visit 23), Day 397 (Visit 25), and Day 399 (Visit 27) in Year 2
Serum creatinine	Baseline Visit, Day 2 and Day 4 (Visits 2, 4 and 5) in Year 1 Day 390 to Day 393 (Visits 20 to 22) in Year 1
Local Laboratory for Japan Only	
Local labs as described above	Day 2 to Day 10 (Visit 4 to Visit 10) in Year 1 Day 391 to Day 399 (Visits 21 to 27) in Year 2
Haptoglobin	Day 2 and Day 4 (Visit 4 and Visit 5) in Year 1 Day 391 and Day 393 (Visits 21 and 22) in Year 2
Local Laboratory for Russia Only	
Chemistry and hepatic safety	Baseline (Visit 2), Day 2 to Day 240 (Visit 4 to Visit 17) in Year 1 ^{d,e} Day 390 to Day 629 (Visit 20 to Visit 34) in Year 2 ^{d,e}
Hematology	Screening Visit (Visit 1), Day 2 to Day 21 (Visit 4 to Visit 12), Day 34 (Visit 13), Day 60 (Visit 14), Day 90 to Day 240 (Visit 15 to Visit 17) and Day 360 (Visit 19) in Year 1 ^f Day 391 to Day 410 (Visit 21 to Visit 29), Day 423 (Visit 30), Day 449 (Visit 31) and Day 479 to Day 629 (Visit 32 to Visit 34) in Year 2

Table 2. Protocol Required Safety Laboratory Assessments

Cystatin C (when possible)	Day 2 to Day 240 (Visit 4 to Visit 17) in Year 1 Day 390 to Day 629 (Visit 20 to Visit 34) in Year 2
GLDH (when possible)	Day 2 to Day 240 (Visit 4 to Visit 17) in Year 1 Day 390 to Day 629 (Visit 20 to Visit 34) in Year 2
Urinalysis	Day 1 to Day 21 (Visit 3 to Visit 12) in Year 1 Day 390 to Day 410 (Visit 20 to Visit 29) in Year 2
Cardiac I, (or cardiac troponin T if cardiac troponin I is not available)	Baseline Visit (Visit 2), Day 2 (Visit 4), Day 4 (Visit 5), Day 6 (Visit 6), Day 8 (Visit 8), and Day 10 (Visit 10), Day 21 to Day 120 (Visit 12 to Visit 16) in Year 1. Day 390 to Day 509 (Visit 20 to Visit 33) in Year 2
Coagulation	Screening Visit (Visit 1), Day 2 to Day 21 (Visit 4 to Visit 12), Day 34 (Visit 13), Day 60 (Visit 14), Day 90 to Day 240 (Visit 15 to Visit 17) in Year 1 Day 391 to Day 410 (Visit 21 to Visit 29), Day 423 (Visit 30), Day 449 (Visit 31) and Day 479 to Day 629 (Visit 32 to Visit 34) in Year 2
Central Laboratory	
Clinical safety (not for Japan)	Days 2 and 4 (Visits 4 and 5) in Year 1 Days 391 and 392 (Visits 21 and 22) in Year 2
Chemistry and hepatic safety (not for Japan)	Days 2 and 4 (Visits 4 and 5) in Year 1 Days 391 and 392 (Visits 21 and 22) in Year 2
Urinalysis (not for Japan)	Days 2 and 4 (Visits 4 and 5) in Year 1 Days 391 and 392 (Visits 21 and 22) in Year 2
GLDH	Day 9 (Visit 9) at Year 1 Day 398 (Visit 26) at Year 2
C3, C4	Days 6 to 10 (Visits 6 to 10) at Year 1 Day 395 to 399 (Visits 23 to 27) in Year 2
Cardiac troponin I	Day 7 (Visit 7) at Year 1 Day 396 (Visit 24) at Year 2

- a. Only if urine dipstick is positive for blood, protein, nitrites or leukocyte esterase. Culture to be done locally.
- b. Only for the Screening Visit (Visit 1) and for Day 360 Visit (Visit 19).
- c. Additional biomarkers, such as ferritin, will be included so long as blood volume limits are not exceeded.
- d. Only creatinine is required at Baseline Visit (Visit 2) in Year 1 and on Day 390 (Visit 390) in Year 2.
- e. ALT and AST will not be analyzed locally, those samples will be sent to the central laboratory to prevent the results being shared with the site or the Sponsor (Section 6.3.).
- f. On Day 360 (Visit 19) the results of neutrophils and platelets are considered sensitive clinical data and are not shared with the site or the Sponsor. They will only be shared with the unblinded medical monitor so they can perform the determination of eligibility for Year 2 IP administration (Section 6.3.3). The local laboratories at the Russian sites will follow the same process.

The results reported by the central laboratory and each local laboratory will be converted to conventional units of measurement, if necessary. If there is a local and central laboratory

collection on the same day, the central laboratory value will be used for analysis. These unit-standardized results will be used for analysis purposes.

The following select laboratory parameters will have additional analyses ([Section 6.7.2](#)): GLDH, CK, C3, C4, creatinine, platelets, and cardiac Troponin I (cTn-I)

3.5.3. Other Safety Endpoints

1. Complete physical examination and brief physical examination

If any finding on the physical examination is considered by the investigator to be ‘clinically significant’, the event is to be recorded as an AE, as appropriate.

2. Complete neurological examination and brief neurological examination

If any finding on the neurological examination is considered by the investigator to be ‘clinically significant’, the event is to be recorded as an AE, as appropriate.

3. Vital Signs

Vital sign parameters include body weight, height, body temperature, pulse rate, respiratory rate, O2 saturation (during 7-day hospitalization post IP administration), and supine blood pressure (systolic and diastolic).

4. Electrocardiogram (ECG)

A single 12-Lead ECG produces the following parameters, as assessed by a central reader: heart rate, PR, QT, corrected QT intervals (ie, QTcF corrected using Fridericia’s formula), and QRS complex.

5. Echocardiogram

The parameters from the echocardiogram include:

- LV Fractional Shortening: (%)
- LVEF: %
- Myocardial longitudinal strain -Global: %
- Myocardial circumferential strain – Global: %
- LV mass (g)
- LV end diastolic and end systolic volume (mL)
- Wall motion abnormalities (normal/ Hypokinetic/ Hyperkinetic/ Dyskinetic/ Akinetic/ Indeterminate)

- Location: LV Basal Anteroseptal, LV Mid Anteroseptal, LV Basal Inferolateral, LV Mid Inferolateral, LV Basal Inferoseptal, LV Mid Inferoseptal, LV Apical Septal, LV Basal Anterolateral, LV Mid Anterolateral, LV Apical Lateral, LV Basal Inferior, LV Mid Inferior, LV Apical Inferior, LV Basal Anterior, LV Mid Anterior, LV Apical Anterior.
- Wall thickness (mm)
 - Location: Interventricular Septum, LV Basal Inferolateral
- Pericardial effusion (present/absent)
 - Location: Pericardial Effusion Indicator: Present, Absent, Not Evaluable
- Pericardial effusion, thickness (mm)

6. Cardiac MRI

The parameters from the cardiac MRI include:

- LVEF (%)
- Myocardial strain parameters include:
 - Global longitudinal strain (%)
 - Global circumferential strain (%)
 - Global radial strain (%)

Myocardial strain measures the degree of myocardial deformation from relaxed to contractile state and is expressed as a percentage. Following the different directions in which the myocardium deforms, longitudinal, circumferential and radial strain can be calculated. Longitudinal strain represents the longitudinal shortening from the base to the apex, and it is expressed by negative values. Circumferential strain represents the shortening along the circular perimeter, and it is consequently represented by negative values. Radial strain is the thickening myocardial deformation towards the center of the left ventricular cavity, and it is expressed by positive values.

- Myocardial fibrosis as assessed by number of LGE positive segments

Participants who have a contraindication to the use of gadolinium will be allowed to have an MRI without contrast. In this case, number of LGE positive segments will be missing.

7. Child Behavior Check List (CBCL)

The Child Behavior Check List (CBCL) is a questionnaire designed to assess behavior problems and social competency in children. There are two versions: the 100-item pre-school questionnaire for ages 1.5 to 5 years, and the 120-item school-age questionnaire for ages 6 to 18 years. For this study, scores on the Withdrawn (pre-school) or Withdrawn/Depressed (school-age) syndrome scale and on the Internalizing global scale (both versions) will be examined as high-risk behaviors or dysfunction. Higher scores on the CBCL indicate higher levels of problematic behaviors or dysfunction. The CBCL scoring algorithm allows for a participant's scores to be standardized using scores from a normal population. These standardized scores are referred to as T-scores. A threshold of ≥ 65 on the T-scores for the Withdrawn and Withdrawn/Depressed syndrome scales and a threshold of ≥ 60 on the and Internalizing global scale indicate clinically significant behaviors.

The specific binary endpoints to be assessed are:

- Withdrawn T-score or Withdrawn/Depressed Syndrome T-Score ≥ 65 ;
- Internalizing Global Scale T-Score ≥ 60 .

8. Investigational Product Administered

The three endpoints below will be used to describe the amount of IP administered.

- The actual total administered dose of fordadistrogene movaparvovec in vg will be calculated as

$$\begin{aligned} &\text{Actual total administered dose (vg)} \\ &= \text{planned dose (vg)} * \frac{\text{administered volume (ml)}}{\text{planned volume (ml)}} \end{aligned}$$

- The actual administered dose of fordadistrogene movaparvovec in vg/kg will be calculated as

$$\text{Actual administered dose (vg/kg)} = \frac{\text{actual total administered dose (vg)}}{\text{weight at Baseline (kg)}}$$

- The percent of planned dose administered will be calculated as

$$\begin{aligned} &\text{Percent planned dose administered (\%)} \\ &= 100\% \frac{\text{actual total administered dose (vg)}}{\text{planned dose (vg)}} \end{aligned}$$

Note that the administered volume will be less than the planned volume if the infusion is stopped prematurely.

